6.6.2. Serious Adverse Event

The definitions and reporting requirements of Health Canada/the Food and Drug Administration (FDA)/ICH Guidelines for Clinical Safety Data Management, Definitions and Standards for Expedited Reporting, Topic E2A will be adhered to. If any AEs are serious, as defined by ICH Guidelines for Clinical Safety, required procedures will be followed.

All SAEs will be reported to the Sponsor via fax or e-mail within 24 hours of becoming aware of the event, whether or not the SAEs are deemed drug-related. refer to the Safety Reporting Instructions for details on how to submit the SAE Report. All serious event reporting will adhere to ICH E6: Guideline for Good Clinical Practice and ICH E2A: Clinical Safety Data Management: Definitions and Standards for Expedited Reporting.: The IRB will be notified of the Alert Reports as per FDA, ICH and the IRB's policies and procedures.

An SAE is any AE that in the view of either the PI or Sponsor, results in any of the following outcomes: Death, a life-threatening AE, inpatient hospitalization or prolongation of existing hospitalization, a persistent or significant incapacity or substantial disruption of the ability to conduct normal life functions, or a congenital anomaly/birth defect. Important medical events that may not result in death, be life-threatening, or require hospitalization may be considered serious when, based upon appropriate medical judgment, they may jeopardize the subject and may require medical or surgical intervention to prevent one of the outcomes listed in the above definition. Examples of such medical events include allergic bronchospasm requiring intensive treatment in an emergency room or at home, blood dyscrasias or convulsions that do not result in inpatient hospitalization, or the development of drug dependency or drug abuse.

Life-threatening is defined as an AE that in the view of the PI or Sponsor, places the subject at immediate risk of death. It does not include an AE that, had it occurred in a more severe form, might have caused death.

Hospitalization does not include the following:

- Rehabilitation facilities, hospice facilities or respite care (e.g. caregiver relief)
- Nursing homes or skilled nursing facilities
- Emergency room visits
- Same day surgeries (as outpatient/same day/ambulatory procedures)
- <24 hour admissions for observation or evaluation

Hospitalization or prolongation of hospitalization in the absence of a precipitating, clinical AE is not in itself an SAE. Examples include:

- Admission for treatment of a preexisting condition that did not worsen
- Hospitalizations for cosmetic elective surgery, social, and/or convenience admissions
- Pre-planned treatments or surgical procedures should be noted in the Day 1 documentation for the individual subject.
- Diagnostic and therapeutic procedures, such as surgery, should not be reported as AEs; however, the medical condition for which the procedure was performed should be reported if it occurs during the reporting period and meets the definition of an AE. For example, an acute appendicitis that begins during the AE reporting period should be reported as an AE, and the resulting appendectomy should be recorded as treatment of the AE.

Unexpected is defined as an AE that is not listed in the IB or is not listed at the specificity or severity that has been observed; or is not consistent with the risk information described in the general investigational plan or elsewhere in the current IND/CTA.

If a SAE occurs to a subject on this study, contact the Medical Monitor within one business day of knowledge of event.

6.6.3. Suspected Unexpected Serious Adverse Reaction (SUSAR)

This is defined as a serious adverse reaction, the nature or severity of which is not consistent with the known study treatment information. A serious event or reaction is not defined as a SUSAR when: 'it is serious but expected' or it does not fit the definition of an SAE, whether expected or not.

6.6.4. Safety Review

At each follow-up visit, subjects will be queried with an open-ended question such as: 'How have you been feeling since your last visit?' Additionally, the study staff will review subject diaries and, if it appears that a potential AE was recorded, study staff will query the subject and determine if an AE occurred.

AEs (whether serious or non-serious) and clinically significant abnormal laboratory test value(s) will be evaluated by the Investigator and treated and/or followed up for up to one month after end of treatment until the symptoms or value(s) return to normal, or acceptable levels, as judged by the Investigator.

Where appropriate, medical test(s) and/or examination(s) will be performed to document resolution of event(s). Outcome may be classified.

6.6.5. Adverse Event Reporting

The Investigator will review each event and assess its relationship to drug treatment (unrelated, unlikely, possibly, probably, likely). Each sign or symptom reported will be graded on the most current version of the NIH NCI CTCAE toxicity grading scale 5-point severity scale (Grade 1, 2, 3, 4 and 5). The date and time of onset, time relationship to drug dosing, duration, and outcome of each event will be noted.

The relationship of each AE to the IP will be assessed using the following definitions:

Unrelated	
• The AE must clearly be caused by the subject's clinical state, or the study procedure/conditions.• Definitely not related to drug.• Temporal sequence of an AE onset relative to administration of drug not reasonable.• Another obvious cause of an AE.
Unlikely	
• Time sequence is unreasonable.• There is another more likely cause for an AE.
Possibly	
• Corresponds to what is known about the drug.• Time sequence is reasonable.• Could have been due to another equally, likely cause.
Probably	
• Is a known effect of the drug.• Time sequence from taking drug is reasonable.• Ceases on stopping the drug.• Cannot be reasonably explained by the known characteristics of the subject's clinical state.
Likely	
• Is a known effect of the drug (e.g., listed in Physicians' Desk Reference, Compendium of Pharmaceuticals and Specialties, IB).• Time sequence from taking drug is reasonable.• Event stops upon stopping drug, event returns upon restarting drug.

The following CTCAE toxicity grading scale 5-point severity scale definitions for rating maximum severity will be used:

Grade 1	Mild; asymptomatic or mild symptoms; clinical or diagnostic observations only; intervention not indicated.
Grade 2	Moderate; minimal, local or noninvasive intervention indicated; limiting age-appropriate instrumental activities of daily living.*
Grade 3	Severe or medically significant but not immediately life-threatening; Hospitalization or prolongation of hospitalization indicated; disabling; limiting self-care activities of daily living.** Note: An experience may be severe but may not be serious, e.g., severe headache).
Grade 4	Life-threatening consequences; urgent intervention indicated.
Grade 5	Death related to AE.

Note: A semi-colon indicates 'or' within the description of the grade.

*Instrumental activities of daily living refer to preparing meals, shopping for groceries or clothes, using the telephone, managing money, etc.

**Self-care activities of daily living refer to bathing, dressing and undressing, feeding self, using the toilet, taking medications, and not bedridden.

AEs will be coded using the most current MedDRA® version available at the start of the study (e.g., 21.0 or higher).

6.7. Reporting Pregnancy

During study participation, all subjects should be instructed to contact the Investigator immediately if they suspect they might be pregnant (e.g., missed or late menstrual period). If pregnancy is confirmed, Investigational Product must be discontinued immediately, the subject should be referred to an obstetrician experienced in reproductive toxicity for evaluation and counseling, and the subject should be followed until the conclusion of the pregnancy.

The Investigator is responsible for reporting all available pregnancy information on the pregnancy report and submitting to the Medical Monitor within 24 hours of becoming aware of the event, although pregnancy itself is not considered an AE. Follow-up information detailing the outcome of the pregnancy and the health of the newborn should be reported as it becomes available. In addition, any pregnancy resulting in a congenital abnormality or birth defect of the newborn, or neonatal death occurring within 30 days of the birth must be reported as a SAE, regardless of causality. Any infant death that occurs after the 30-day reporting period that the Investigator suspects is related to the Investigational Product must also be reported as a SAE.

Partner pregnancies of a male subject do not need to be reported.

6.8. Treatment Stopping Rules

If a subject has non-cutaneous adverse events of concern, clinically significant laboratory values or any condition that the Investigator determines could possibly be related to the IP, the Investigator should immediately contact the Medical Monitor to discuss if the subject should be discontinued from the investigational product.

Treatment for any individual subject will be discontinued if the subject:

- Experiences a serious adverse event (SAE) or a clinically significant non-serious AE which in the opinion of the Principal Investigator or Medical Monitor warrants discontinuation from the IP for that subject's well-being.
- A severe (Grade 3) laboratory abnormality (confirmed by repeat sample and considered related to IP).

Dosing of IP for an individual subject may be suspended for safety concerns other than those described above, at the discretion of the Investigator if he/she feels the subject's safety may be threatened.

A subject with a PHQ-8 or modified PHQ-A score of 15 or above should be referred promptly to a mental health care professional and consideration be given to discontinuation from IP.

A subject with a CDI-2 raw total score of 32 or above should be referred to a mental health professional, and Investigators in consultation with the mental health professional should consider interruption or discontinuation of the IP.

- Subjects with a CDI-2 raw score of 21 or above in females and 22 or above in males should be referred to a mental health professional for evaluation

A subject that is experiencing suicidal ideation and behavior should be referred immediately to a qualified mental health care provider and consideration given to discontinuation from IP.

As noted above, study treatment must be discontinued immediately in the event of a female subject's pregnancy.

Treatment should be interrupted:

- If a subject develops an application site reaction with the clinical appearance of an 'irritation reaction', and with a severity of a Dermal Response Score of 5 (erythema, edema and papules) or greater on the scale of Berger and Bowman, treatment should be interrupted for up to one week and may then be resumed if the reaction has, in the opinion of the Investigator, adequately resolved.

Treatment should be discontinued:

- If the reaction reoccurs, treatment should be discontinued permanently, and the subject followed until the reaction resolves. Given the excellent local toleration in the Phase 1/2a study, such reactions are possible, but unlikely.

7. DATA ANALYSIS

Data will be handled and processed according to the Contract Research Organization's Standard Operating Procedures, which are written based on the principles of GCP.

7.1. Statistical Methods

The methodology presented below is a summary of the more detailed analysis plan that will be presented in the Statistical Analysis Plan (SAP). The SAP will be finalized before the database is locked and unblinded. Any changes to the methods described in the final SAP will be described and justified in the clinical study report.

All statistical processing will be performed using SAS® (Version 9.4 or later) unless otherwise stated.

Descriptive statistics will be used to provide an overview of the safety and efficacy results. For categorical parameters, the number and percentage of subjects in each category will be presented. The denominator for percentage will be based on the number of subjects appropriate for the purpose of analysis. For continuous parameters, descriptive statistics will include n (number of subjects), mean, standard deviation (SD), median, Q1, Q3, minimum, and maximum.

No missing efficacy or safety data will be imputed unless specified otherwise. The observed values will be used in the analysis.

The final analysis will be conducted after all treated subjects in Cohort 1 Group 1 and Cohort 2 have had the opportunity to be followed to the Week 52 assessment. Once all treated subjects in Cohort 1 Group 2 have had the opportunity to be followed to the Week 52 assessment, listings for these subjects will be provided for the CSR addendum.

7.1.1. Baseline Definition

For subjects in Cohort 1, the baseline value for safety and efficacy parameters will be defined as the last observation prior to the first dose of ARQ-154 foam 0.3% in either the prior ARQ-154 study or this study (See [Section 7.2.1](#) for the definition of a treatment emergent event).

Additional analyses will be performed where the baseline value for subjects in Cohort 1 is defined as the last observation prior to the first dose of ARQ-154 foam 0.3% in this study. For the purpose of these latter analyses, study procedures will not be repeated; the information from the prior ARQ-154 study final visit will be carried over to the Day 1 visit for this study.

For subjects in Cohort 2, baseline values for efficacy and safety will be defined as the last observation prior to the first dose of ARQ-154 foam 0.3% in this study.

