^k For Cohort 1, the consent will be signed after completion of the final visit in prior ARQ-154 study. Cohort 2 will sign consent prior to any study-related procedures at the Screening Visit.

- ^l For Cohort 1, this data will be obtained from the final visit of the prior ARQ-154 Study and used as the Day 1 data for this long-term safety study (ARQ-154-214). If after the prior ARQ-154 study completion, subjects should complete the screening visit procedures. The Baseline values for Safety tabulations will be taken from the day that the subject received their first active IP (across prior ARQ-154 studies and ARQ-154-214). Baseline values for efficacy will be those recorded on Day 1 of the prior ARQ-154 Study. For Cohort 2, Baseline evaluations will be obtained for all procedures and the Baseline/Screening version of the C-SSRS will be utilized at Screening. For Cohort 2, Screening labs that are collected within 14 days of Day 1 do not need to be repeated.
- ^m For Cohort 2 adolescent subjects PK samples will be collected on Week 4 for adolescent subjects between 12 – 16 years old. Collect PK sample with the safety lab collection. Ensure PK will not be drawn on the area where investigational product is applied.
- ⁿ At select sites, the Investigator will collect samples for *Malassezia* testing on Cohort 1 Group 2 subjects at Weeks 4, 12, 24, 36, and 52. Samples will be collected from treated and untreated areas by swabbing the skin surface. Samples should be collected from the same areas as samples collected during the ARQ-154-116 Baseline visit.

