6.1. Statistical Definitions and Algorithms

6.1.1. Baseline

There are three baseline definitions for the analyses:

- Primary baseline is defined as the last observation before the first dose of roflumilast foam 0.3% in either ARQ-154 parent study or this study for subjects administered vehicle previously.
- Open-label baseline (OLE baseline) is defined the last observation before the first dose of roflumilast foam 0.3% in this study. For subjects in Cohort 1 who choose to enroll in this study, study procedures will not be repeated; study sites will carry over the information from the prior ARQ-154 study to the Day 1 visit for this study. For subjects in Cohort 2 Group 4, the definition for Primary and OLE baseline is the same.
- Safety baseline is defined as primary baseline for Cohort 1 Group 1, and OLE baseline for Cohort 2 Group 3 and Group 4.

The following table described the baseline used in the analysis:

Cohort Groups	Prior therapy, medical history	Demog and Efficacy Analysis	Safety Analysis for AE, PHQ8, PHQ-A, Prior and Concomitant medications	Safety Analysis for lab, vital signs and tolerability assessments
Cohort 1 Group 1	OLE baseline	Primary baseline and OLE baseline	OLE baseline	Primary baseline
Cohort 2 Group 3	OLE baseline	Primary baseline and OLE baseline	OLE baseline	OLE baseline
Cohort 2 Group 4	OLE baseline	Primary baseline and OLE baseline	OLE baseline	OLE baseline
Cohort 2 Total	OLE baseline	Primary baseline and OLE baseline	OLE baseline	OLE baseline

Overall	OLE baseline	Primary baseline and OLE baseline	OLE baseline	Safety baseline of roflumilast foam 0.3% in this study for subjects in the safety analysis population. For subjects in Cohort 2 Group 4, the definition for Primary and OLE Baselines is the same
----------------	--------------	-----------------------------------	--------------	---

Baseline values will most commonly be from Day 1.

For subject tolerability assessments, baseline is derived as the last non-missing measurement taken on the day of first application of study drug.

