- **PHQ-8** = sum of the 8 questions (individual questions scored as Not at all=0, Several days=1, More than half the days=2, and Nearly every day=3; range for score 0 to 24). If more than 1 item is missing the score should not be calculated. If 1 item is missing the score is calculated as (sum of answered items*8)/number of answered items.
- **PHQ-A** = sum of the 8 questions (individual questions scored as Not at all=0, Several days=1, More than half the days=2, and Nearly every day=3, (range for score 0 to 24). If more than 1 item is missing, the score should not be calculated. If 1 item is missing, the score is calculated as (sum of answered items*8)/number of answered items.
- **CDI-2** = total score is calculated as a sum of the 17 questions (individual questions scored as much or most of the time=3, often=2, some of the time=1, Not at all=0; range for score 0 to 51).
 - CDI-2 emotional problem scale is a sum of 9 questions (Q1, Q3-6, Q8, Q10 -12)
 - CDI-2 function problem scale is a sum of 8 questions (Q2, Q7, Q9, Q13-17)
- **Scalpdex score transformation** = Scalpdex is rated on a 1 to 5 scale which will be transformed to 0 to 100 Scale where 1=0; 2=25; 3=50; 4=75; 5=100. This transformed score is used to calculate scale scores.
- **Scalpdex Emotions Scale** = average of (Q2, Q4, Q5, Q6, Q7, Q9, Q10, Q11, Q12, Q14, Q16, Q17, Q19, Q20, Q22) after transforming to 0 to 100 scale as mentioned above.

Q refers to question number. Q19 will be reverse scored i.e., 1=100; 2=75; 3=50; 4=25; 5=0.

- **Scalpdex Symptoms Scale** = average of (Q1, Q3, Q8) after transforming to 0 to 100 scale as mentioned above. Q refers to question number.
- **Scalpdex Functioning Scale** = average of (Q13, Q15, Q18, Q21, Q23) after transforming to 0 to 100 scale as mentioned above. Q refers to question number.
- **Scalpdex Total Score** = calculated as mean of all the 23 scalpdex questions using the transformed scale of 0 to 100. Q19 will be reverse scored i.e., 1=100; 2=75; 3=50; 4=25; 5=0 while calculating the mean. Q refers to question number.
- **Total % BSA (body surface area)** = sum of coverage areas of head, limbs, upper limbs, and lower limbs.
- **Change from baseline** = value at current time point – value at baseline. This is derived separately for primary baseline and OLE baseline.
- **Percent change from baseline** = (value at current time point – value at baseline)/value at baseline. This is derived separately for primary baseline and OLE baseline.

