9.1. Adverse Events

All AEs will be coded using the MedDRA dictionary version 24.1 or above.

A TEAE is defined as an AE that started after application of IP at the Baseline Visit in this extension study. All TEAEs will be summarized from OLE baseline.

An overall summary of TEAEs will be provided; this will present number and percent of subjects who reported at least 1: TEAE (including all TEAEs, TEAEs by maximum severity, and TEAEs by greatest relationship), treatment emergent SAE (TESAE), TEAE leading to study drug withdrawal, TEAE leading to study withdrawal, or TEAE resulting in death.

The number and percent of subjects reporting TEAEs, grouped by MedDRA system organ class (SOC) and preferred term (PT), will be tabulated by all TEAEs, non-serious TEAEs, maximum severity, or greatest relationship to study IP; Cohort and by groups and overall. In the case of multiple occurrences of the same TEAE within the same subject, each subject will only be counted once for each preferred term.

The number and percent of subjects reporting TEAEs will be tabulated by PT and presented by groups and overall.

In the summaries showing severity and relationship to study medication, the event with the maximum severity (mild < moderate < severe) or strongest relationship (not related < related) will be reported. If a particular event is missing the severity and/or relationship, then the strongest possible severity or relationship will be assumed for analysis (severity = severe, relationship = likely).

All the AEs will be listed. The AEs that are treatment emergent will be flagged. Any AEs related to the application site will be flagged in the listing.

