9.3. Clinical Laboratory Evaluations

Laboratory test results will be summarized descriptively by groups and study visit as both observed values, changes, and percent changes from baseline values for continuous hematology, chemistry, and urinalysis results. Categorical urinalysis results will be summarized using frequencies by groups and study visit.

The number of subjects with clinical laboratory values below, within, or above the normal range by study visit and in relation to baseline will be tabulated for each clinical laboratory analyte (shift table).

Primary baseline will be used for Cohort 1 Group 1 and OLE baseline for Cohort 2. Overall group will be summarized using Safety baseline.

Abnormal laboratory values will be presented in the listings.

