9.4. Vital Signs

Descriptive summaries of observed values, changes, and percent changes from baseline will be calculated for systolic blood pressure, diastolic blood pressure, heart rate, height, weight, body mass index, and oral body temperature by group and study visit.

Categorical percent changes in weight (i.e., shifts from baseline) by group will be summarized by the number of subjects who gain or lose $\geq 5\%$ of their baseline body weight during the course of the study, as well as subjects who gain or lose $\geq 10\%$ of their baseline body weight over the course of the study by groups and study visit.

BMI is derived as specified in Section [6.1.7](#). Shift tables for subjects who shift from their baseline BMI category (underweight, normal, overweight, obese) to a different BMI category throughout the course of the study will be provided by groups and study visit.

Shift tables for weight and BMI will also be summarized by intentional and unintentional weight loss (defined from question on vital sign eCRF). Vital signs summaries will use primary baseline for Cohort 1 Group 1 and OLE baseline for Cohort 2. Overall group will be summarized using Safety baseline.

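### Laboratory, vital-sign, weight and BMI tables for Cohort 1 Group 1 lack the additional Day 1 (OLE) baseline view that Protocol 7.1.1 plans, and the SAP does not record the omission

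*Protocol*

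**What the plan says.** Protocol 7.1.1 has two steps for Cohort 1. First, "the baseline value for safety and efficacy parameters will be defined as the last observation prior to the first dose of ARQ-154 foam 0.3"%, whether that dose fell in the prior study or in this one. This is what the SAP calls primary baseline. Second, "Additional analyses will be performed where the baseline value for subjects in Cohort 1 is defined as the last observation" before the first dose in this study, with the prior study's final-visit data carried over to Day 1. This is the SAP's OLE baseline. The second step names no data domain and excludes none.

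Footnote l to the schedule in Protocol 1.3 supports the first step: "The Baseline values for Safety tabulations will be taken from the day that the subject received their first active IP", counted across studies.

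The baseline table in SAP 6.1.1 gives both baselines for demographics and efficacy. Under the column "Safety Analysis for lab, vital signs and tolerability assessments" it gives Cohort 1 Group 1 primary baseline only. The text repeats this:

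- SAP 9.3, laboratory: "Primary baseline will be used for Cohort 1 Group 1 and OLE baseline for Cohort 2".
- SAP 9.4, vital signs, weight and BMI: "Vital signs summaries will use primary baseline for Cohort 1 Group 1 and OLE baseline for Cohort 2".

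SAP 6.1.7 nevertheless says of change and of percent change from baseline: "This is derived separately for primary baseline and OLE baseline". SAP section 10 lists five changes from the planned analysis, and this is not among them.

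**The concern.** The objective is long-term safety over up to 52 weeks in this study, and Protocol 3.3.2 names weight loss among the most common adverse events of oral roflumilast. A reader will want to know how many subjects developed an out-of-range laboratory value, or lost 5% or 10% of body weight, after entering this study.

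For subjects who rolled over directly from active foam, a primary-baseline shift table answers a different question: what has changed since the start of ARQ-154-203. Both questions are legitimate, and Protocol 7.1.1 appears to provide for both. The SAP tabulates only the cumulative one for these data, and gives no reason.

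**Working it through.** **1. Who is affected.** SAP section 8 states that for prior-vehicle subjects and de novo subjects the two baselines coincide. SAP 6.1.1 already uses OLE baseline for all of Cohort 2 in these tables. That leaves Cohort 1 Group 1 subjects who received roflumilast in ARQ-154-203. SAP section 6 displays Group 1 as Roflumilast, Vehicle and Total, so the affected columns are Group 1 Roflumilast, Group 1 Total and Overall. In Overall, the prior-roflumilast Group 1 subjects are measured from the parent study and everyone else from entry to this study.

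**2. How far apart the baselines are.** Target days for prior-roflumilast subjects come from SAP Table 2 (primary baseline) and Table 3 (OLE baseline). Offset = Table 2 day - Table 3 day. Share before rollover = offset / Table 2 day.

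| Visit | Primary | OLE | Offset | Share before rollover |
|---|---|---|---|---|
| Week 4 | 85 | 29 | 56 | 66% |
| Week 12 | 141 | 85 | 56 | 40% |
| Week 24 | 225 | 169 | 56 | 25% |
| Week 36 | 309 | 253 | 56 | 18% |
| Week 52 | 421 | 365 | 56 | 13% |

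The offset is 8 weeks throughout.

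**3. Effect on a weight threshold.** SAP 9.4 counts gains or losses of at least 5% and at least 10% of baseline weight. The weights below are assumed, not taken from the documents. Percent change = 100 x (visit weight / baseline weight - 1).

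- 80.0 kg at parent Day 1, 82.5 kg at rollover, 78.0 kg on study. From primary: 78.0/80.0 - 1 = -2.5%. From OLE: 78.0/82.5 - 1 = -5.5%. An on-study loss of more than 5% is not counted.
- 80.0, 76.5, 75.9 kg. From primary: 75.9/80.0 - 1 = -5.1%. From OLE: 75.9/76.5 - 1 = -0.8%. A subject is counted although nearly all the loss preceded this study.

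**4. Effect on a laboratory shift.** The same logic applies without arithmetic. A value that was normal at parent Day 1, abnormal at rollover and still abnormal afterwards appears as a shift at every visit from primary baseline, and as no shift from OLE baseline. A value that was abnormal at parent Day 1, normal at rollover and abnormal again in the same direction on study does the reverse.

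**5. What can be recovered.** Table 2 includes ARQ-154-203 Week 8. If that row is shown for safety data, the mean change since rollover can be approximated by subtraction. Shift and threshold counts cannot be obtained this way, because they depend on each subject's own pair of values.

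**The case against.** The strongest counter-argument is that the SAP follows the protocol. Protocol 7.1.1 and footnote l both place the safety baseline at the first active dose, the sentence on additional analyses names no safety domain, and the SAP does use OLE baseline for Cohort 1 efficacy, adverse events, PHQ-8, PHQ-A, CDI-2 and C-SSRS. Cumulative exposure is also a deliberate view: SAP 7.6 summarises duration from both baselines, and a weight loss that began on active foam in ARQ-154-203 is a genuine on-drug loss. All of this stands. It shows that the primary-baseline tables should remain. It does not explain why the second view is absent for these data, since the sentence follows directly on one covering safety and efficacy and is not restricted.

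A reader might infer several stronger things that the documents do not support:

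- *That on-study change cannot be separated anywhere in Cohort 1.* Prior-vehicle subjects have a single baseline and their own column. For prior-roflumilast subjects, observed values are tabulated by visit and abnormal laboratory values are listed.
- *That tolerability is affected too.* SAP 9.2 summarises the scores themselves, with no change or shift table, so the choice of baseline hardly matters.
- *That the differing time zeros are a SAP error.* In SAP 9.1, "All TEAEs will be summarized from OLE baseline", while laboratory shifts run from primary baseline. The protocol has the same arrangement: Protocol 7.2.1 counts events from first treatment in this study.
- *That a large share of weight losses would be missed.* Take independent normal weight changes with mean zero, SD 1.5, 2 or 2.5% in the parent study and 3, 4 or 5% here. Then 24%, 22% or 21% of subjects losing at least 5% on study are missed from primary baseline. As a share of all prior-roflumilast subjects that is only 1.2%, 2.3% or 3.3%, and primary baseline flags more subjects overall (6.7% v 4.8%, 13.1% v 10.6%, 18.6% v 15.9%). None of these inputs is in the documents.

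**Conclusion.** The point holds in a narrow form. An additional analysis that Protocol 7.1.1 plans without restriction is missing from the SAP for laboratory, vital-sign, weight and BMI data in Cohort 1 Group 1, and the omission is unrecorded. The consequence is confined to prior-roflumilast subjects in that group and the two summary columns containing them. For them, on-study laboratory shifts, weight-threshold counts and BMI-category changes cannot be read from the planned tables.

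The 56-day offset follows from the SAP's own tables. The weight examples show that misclassification can go either way, but not how often it will. The documents do not give the number of prior-roflumilast subjects in Group 1 or the variability of their weight. The conclusion also assumes that the unrestricted sentence in Protocol 7.1.1 covers safety data. If efficacy alone was meant, the text should say so. The study is descriptive and no primary conclusion is invalidated, so this is a cheap improvement.

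**What to change.** In SAP 6.1.1, 9.3 and 9.4, add OLE-baseline versions of the laboratory change and shift tables, the vital-sign change tables, and the weight-category and BMI-category tables, for Cohort 1 Group 1 (by prior treatment and total) and Overall. Keep the primary-baseline versions as the main display, and state the baseline in each title. SAP 9.2 needs no change. If the sponsor decides against the added tables, SAP section 10 should record and justify the departure from Protocol 7.1.1. That settles traceability but does not supply the missing counts.

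The cost is SAP wording and a second run of existing table programs with the other baseline flag. The change variables (SAP 6.1.7), the OLE visit windows (SAP Table 3) and the carried-over Day 1 values (Protocol 1.3, footnote l) are already provided for, so no new data are needed. The downside is a longer set of tables.
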